An involuntary early pregnancy loss, or miscarriage, occurs in about 20% of pregnancies (Quenby *et al.*, 2021), catching parents by surprise and often resulting in long periods of grief and psychological stress (Brier, 2008; deMontigny *et al.*, 2017). In the present study, we define early pregnancy loss as a loss that occurs in the first 20 weeks of gestation. A gestational loss, even in the earliest stages, can lead to chronic grief that goes on for years, not showing the typical decline of grief seen in other situations, even after the birth of another child (Markin, 2017). However, despite the high incidence of miscarriages, parents' psychological distress is often devalued (Radford & Hugues, 2015; Bellhouse *et al.* 2018), leading to an increase in feelings of isolation and implying a high risk for the development of psychological disorders (Kulathilaka *et al.* , 2016; Farren *et al.* , 2020). A recent study of 492 women who experienced an early pregnancy loss showed that after one month, 29% had symptoms of post-traumatic stress, 24% symptoms of moderate/severe anxiety, and 11% symptoms of moderate/severe depression; these decreased over time but were still clinically relevant nine months after the loss (Farren *et al.* , 2020). It should be noted that satisfaction with health services regarding loss management is crucial for a faster resolution of psychological distress. A study examining the impact of satisfaction with health services on the duration of grief symptoms showed that women dissatisfied with the treatment they received still had grief symptoms two years after the loss (deMontigny *et al.* , 2017).

The high incidence of psychological morbidity after a miscarriage highlights the importance of psychological support to manage grief after the event. In fact, several studies have shown a decrease in symptoms of grief, post-traumatic stress, depression and anxiety when women underwent psychological interventions that helped them cope with their losses (Kersting *et al.* , 2013; Johnson & Langford, 2015). Unfortunately, only a limited number of women have access to professional

psychological support after a miscarriage, since this service is often unavailable or unsolicited (Kersting & Wagner, 2012). The use of Information and Communication Technologies (ICT) has great potential to increase access to emotional and psychological support. In the literature, only a limited number of studies explored the use of ICTs applied to post-gestational loss support, all were via the internet, but the results are very encouraging, showing a decrease in symptoms of post-traumatic stress, grief, and depression (Ashford, 2016).

Virtual reality

Virtual Reality (VR) is a technology with a lot of potential that allows the flexible creation of personalized treatment environments based on neuroscientific and clinical guidelines. VR enables the creation of well-controlled simulations oriented to the needs of patients, using feedback and reward mechanisms, and increasing motivation by incorporating treatments into game-like tasks. In addition, it allows you to monitor and quantify the performance and evolution of patients over time. VR has been widely used in mental health interventions directed at different domains, with the most affected disorders being anxiety, substance dependence and eating disorders, with very positive results (Cieślik *et al.*, 2020). In particular, post-traumatic stress disorder is the one that has been most often addressed with VR, usually for exposure treatments after a traumatic event (Eshuis *et al.*, 2021). In this context, VR has the advantage of recreating and exposing patients to traumatic situations in a safe space where their emotions can be freely expressed. The adaptability of VR is also a key feature, as it allows an easy adjustment of interventions through changes in the elements of the simulated environment, as well as adapting the scenarios to the users' individual preferences. In addition, VR has been shown to be clinically appropriate for implementing psychotherapy techniques such as Cognitive Behavioral Therapy (CBT), making it a robust tool for providing such services (Lindner *et al.*, 2019; I want *et al.*, 2019).

Concerning the use of VR for interventions in the area of grief, not necessarily derived from a gestational loss, there is very little work. As far as we know, only one

study addressed the use of VR for patients suffering from complicated grief (grief that does not resolve over time) (Quero *et al.* , 2019) . A CBT protocol was followed using the traditional face-to-face or VR method, and the results were compared at the end of treatment, and at 6 and 12 months of follow-up. Although both methods led to significant improvements over time, the VR group was superior in clinically significant long-term change (Quero *et al.* , 2019) . The VR system used was EMMA's World, a system that has already been used in the treatment of post-traumatic stress and adjustment disorders (Guillén *et al.* , 2018) . The purpose of this system is to help process emotions associated with stressful events using 3D objects, sounds, music, and elements of personal meaning to the user. This system is also currently being used to provide psychological support after pregnancy loss, but at this time, only the protocol has been published (Corno *et al.* , 2020) . Currently, there are no published results on the use of VR systems explicitly targeted for gestational loss.

AViR Project

The AViR project is a project funded by FCT - Foundation for Science and Technology (EXPL/CCI-INF/0298/2021) that aims to fill this gap in the literature by proposing the use of a multi-scenario VR prototype that uses the adaptability of VR and traditional psychological support protocols to provide an adaptable intervention and personalized specifically oriented to grief after an early gestational loss. This prototype encompasses different virtual scenarios to address various aspects of the grief management process. All contents are defined with the collaboration of health professionals with experience in psychological support after gestational loss. The virtual scenarios are implemented in a VR display to increase the level of immersion and presence (Butussi & Chitaro, 2018), allowing the participant to be in a safe space where their emotions can be shared freely.

The present research study proposal aims to evaluate the feasibility of the proposed approach by testing the prototype system in a controlled pilot study with 20 women who suffered an early gestational loss in the last six months. We hypothesize that using the proposed VR paradigm will result in a significant reduction in symptoms

of grief, depression, anxiety, and post-traumatic stress, and that this reduction will be significantly superior when compared to the control group.

The study we propose is very innovative regarding the target population and the use of VR, specifically designed to address gestational loss. In addition, it opens a new avenue of research on a topic that is still silenced and considered taboo in our society. Thus, this interdisciplinary research has an expected scientific, technological, and social impact, namely: 1) contributes to a better understanding of the process of psychological recovery after an early gestational loss; 2) contributes to the advancement of technologies aimed at psychological support; 3) has the potential to accelerate the resolution of grief by bringing emotional and psychological support to women who do not have access to other means of support; and 4) contributes to reducing the economic burden on health care by providing tools to improve the well-being of patients.

GOALS

This study has two main objectives:

- 1) Evaluate the impact of the proposed VR paradigm in women who suffered a gestational loss in the first 20 weeks of gestation, compared to a control group that follows the usual follow-up;
- 2) Evaluate the usability, user experience, and acceptance of the proposed approach.

METHODOLOGY

Sample and recruitment

The target population of this pilot study are women who have suffered involuntary pregnancy loss in the first 20 weeks of gestation. The recruitment of participants will be led by [name], in collaboration with the Obstetrics and Gynecology Service of SESARAM. We intend to recruit a sample of 20 participants who will later be divided into two groups, an intervention group using VR and a control group that will have access to standard monitoring.

Inclusion and exclusion criteria

Considering the objective and target population of the AViR project, the sample will be composed of women who have experienced early gestational loss, meeting the following **inclusion criteria**:

1. Have experienced an involuntary gestational loss in the first 20 weeks of pregnancy, in the last six months;
2. Be at least 18 years of age.

As **exclusion criteria**, we consider the following factors:

1. Have a diagnosis of mental disorder;
2. Be performing psychological intervention;
3. Being pregnant;
4. Having some visual deficit that may interfere with the normal performance of VR tasks.

[figure not shown]
Study design

To test the research hypothesis, the proposed study follows an experimental design, namely, a randomized controlled study with two independent

conditions/groups (VR and Control). Participants who meet the inclusion criteria will be randomly allocated to one of the two groups described.

Data collection procedure

The pilot study will encompass a 4-week intervention and two evaluation moments: pre-intervention (baseline) and post-intervention, in which both groups, VR and Control, will participate. The VR group will have an intervention program lasting four weeks, with three weekly sessions of 45-60 minutes, using the developed prototype.

The VR prototype consists of VR glasses (Oculus Quest 2) where participants will experience different therapeutic modules, the contents of which were developed in collaboration with health professionals with experience in psychological support after pregnancy loss. The four modules cover: 1) **Psychoeducation**, to provide information about the grieving process, its phases, emotional and behavioral manifestations typical of this period; 2) **Validation of loss**, to recognize the loss and allow the performance of farewell and remembrance rituals; 3) Social sharing, to create a safe and judgment-free environment, conducive to sharing the experience

with others; and 4) **Adaptation to loss**, with a narrative that highlights the importance of physical well-being, social contact and the surrounding environment as fundamental elements for a healthy lifestyle. The intervention sessions with VR will be held by the master's student and graduate in Psychology, [name], who will decide which modules to apply in each session depending on each participant's response. The control group will do the standard follow-up, normally provided by SESARAM to this specific population. After the post-intervention evaluation, the control group will be given the possibility to use the VR system for four weeks, as in the case of the VR group.

The pre- and post-intervention evaluation of both groups includes a set of instruments that aim to assess symptoms of grief, depressive and anxious, and post-traumatic stress. The evaluation of usability and user experience will be carried out only by the VR group after the intervention. All evaluations will be carried out by [name]. All participants will be duly informed of the objectives and procedures of the study, and will sign the participant information document and informed consent. The data collection sessions will take place in the spaces designated for this purpose in LifeTech Madeira (<https://lifetech.web.uma.pt>), according to the protocol signed by the University of Madeira and the Regional Secretariat of Health.

Data collection tools

To infer the possible effects of the intervention, all participants will respond to the following instruments validated for the Portuguese population, pre- and post-intervention:

- **Perinatal mourning:** *Perinatal Grief Scale (PGS)*, a version adapted for the Portuguese population (Rocha, 2004).
- **Post-Traumatic Stress:** *Post-traumatic Stress Disorder Checklist (PCL-5)* (DSM-5 (Diagnostic and Statistical Manual of Mental Disorders, 5th edition), Portuguese adaptation (Carvalho *et al.*, 2020) .

- **Depressive and Anxious Symptomatology:** *Hospital Anxiety and Depression Scale* (HADS), version adapted for the Portuguese population (Pais-Ribeiro *et al.*, 2007).

To assess the **usability and user experience** regarding the VR prototype, after the intervention, the participants allocated to the intervention group will complete questionnaires for the corresponding objectives, namely:

- **Usability:** *System Usability Scale* (SUS) (Brooke, 1996).
- **Presence:** *Sense of Presence Inventory* (ITC), adapted for the Portuguese population (Vasconcelos-Raposo *et al.*, 2019).
- **User experience:** a questionnaire with open questions on different aspects related to the experience of using the VR system.

In addition to the instruments mentioned, a **participant form** with relevant socio-demographic and clinical information will also be completed. All the instruments referred to are attached to this document.

Data processing and analysis

The results of this study will be explicitly presented in tables and graphs. In terms of data description, categorical variables will be presented as absolute values or percentages, and quantitative variables will be presented through means, medians, standard deviations and quartiles. Regarding the statistical analysis tests, the chi-square test will be used to compare independent categorical variables; the Student's t-test to compare parametric variables; the Wilcoxon test to compare intra-subject nonparametric variables; and the Mann-Whitney test to compare nonparametric inter-subject variables. Correlations between variables will be performed using Pearson's coefficient for parametric variables and Spearman's coefficient for nonparametric variables. For all statistical comparisons, a significance level of 5% ($p < .05$) will be established. The data will be analyzed through the computer program SPSS 24.0 (IBM, NY, USA).

Dissemination of results

Considering the proposed project and the innovation of the paradigm and the interdisciplinary nature of this work, we aim to produce scientific publications in conferences and journals in the areas of Gynecology and Obstetrics, Psychology, Informatics applied to health, and/or human-computer communication. We also intend to disseminate the results obtained at regional and national level, specifically in health institutions. The goal will be to inform end-users and health professionals of the benefits that a system such as the one proposed can have on the population that has experienced an early pregnancy loss. Dissemination activities will also play an important role in raising awareness of this issue in society in general, thus contributing to increased psychological support interventions.

ETHICS

General considerations

Considering the good research practices by which we guide our scientific work, all the conditions inherent in the ethical principles associated with clinical trials with people will be considered. Since this project aims to carry out a study that involves collecting data on people, processing of personal data and observing patients, the application of appropriate legislation and regulations will be ensured before, during and after the implementation of the study. The protocol that has been detailed here is under the rules and regulations applied in Portugal and Europe. The professionals involved in this project have experience in this area of research and have previously coordinated and executed clinical trials that involved collaborations between universities and hospitals.

The project complies with European standards, such as:

- The Charter of Fundamental Rights of the European Union (in particular Article 3 - right to respect for physical and mental integrity and Article 8 - right to protect personal data).
- Declaration of Helsinki:
 - Directive 2001/20/EC of the European Parliament and Council of 4 April 2001 on the harmonization of laws, regulations and administrative provisions of the Member States concerning the implementation of good clinical practice in conducting clinical trials on medical devices for human use.
 - Council Directive 95/46/EC of the European Parliament and Council of 24 October 1995 for the protection of individuals with regard to the processing of personal data and mobility.
- Treaty on European Union: Article 6.
- Charter of Fundamental Rights of 7 December 2000.
- The project complies with Portuguese standards, such as:
 - Article 35 of the Portuguese Constitution – use of information technologies;
 - Law 67/98 – The Personal Data Protection Act.

Data protection

This protocol is in accordance with the following procedures, with regard to the processing of personal data:

- Data cannot be collected without authorization. Before starting the study, all participants will be informed verbally and in writing of the study's details, including any risk involved. All participants sign an informed consent before participating in the study.

- DBirth minutes and other personal data that can identify the person will be encrypted to protect the privacy of the patient and the data collected.
- All the information obtained will only be used within the project's scope and will not be saved for other purposes.

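### The hypothesis includes a VR-only reduction claim with no comparator, and the between-group tests named take no baseline covariate (minor)

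*Protocol*

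**What the plan says.** The hypothesis closes the Protocol section *AViR Project* and has two joined clauses. The first names no comparator: "We hypothesize that using the proposed VR paradigm will result in a significant reduction in symptoms" of grief, depression, anxiety and post-traumatic stress. The second is comparative: "and that this reduction will be significantly superior when compared to the control group". Objective 1 under *Goals* is also comparative ("compared to a control group that follows the usual follow-up"), and *Study design* presents the two-group randomised design as the means of testing the hypothesis.

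*Data collection procedure* provides "two evaluation moments: pre-intervention (baseline) and post-intervention, in which both groups, VR and Control, will participate". *Data collection tools* introduces the scales with "To infer the possible effects of the intervention, all participants will respond to the following instruments".

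*Data processing and analysis* lists "the Student's t-test to compare parametric variables", without saying whether paired or independent, then "the Wilcoxon test to compare intra-subject nonparametric variables", then Mann-Whitney for comparisons between subjects. All are at 5%. No test is matched to a clause, none takes a covariate, and the section does not say whether post-intervention scores or changes are compared.

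On the natural course, the introduction reports that post-traumatic stress, anxiety and depression symptoms fell over time in a cohort of 492 women but were still clinically relevant at nine months. It describes grief after a gestational loss as possibly not following the usual decline. The entry criterion is "Have experienced an involuntary gestational loss in the first 20 weeks of pregnancy, in the last six months".

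**The concern.** The first clause is worded causally but can be tested inside the VR group alone, and the listed Wilcoxon test would do that. By the protocol's own account, two of the measured areas (PCL-5 and HADS) tend to improve in the months when these women are followed. A significant fall in the VR group could then be reported as a result of VR when the women only followed the course expected under usual follow-up. Looking at the control group's own p-value does not cure this, because in groups of about 10 one arm often reaches significance and the other does not by chance alone.

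The second, separate matter is efficiency. Both groups have baseline scores, yet the between-group tests named do not use them as a covariate. In a trial of 20 women precision is scarce.

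**Working it through.** **Inputs.** From the protocol: 20 women, two randomised groups, 5% level, baseline and post-intervention scores in both groups, entry within six months of the loss, four weeks of intervention. If the intervention starts soon after entry, assessment ends at about 6 + 1 = 7 months after the loss at the latest, before the nine-month point in the introduction. The protocol gives no SD, effect size, power or size of decline, so there is no stated figure to reproduce. Assumed: 10 per arm (the ratio is not given), two-sided tests (sidedness is not given), normal scores.

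**Step 1: the first clause alone, with no VR effect.** Let both arms fall by *d*, in SDs of the change score. For a paired t-test the noncentrality is *d*√10 on 9 df. The Wilcoxon and joint results come from 200,000 simulated trials, with exact two-sided rejection at W+ ≤ 8 for Wilcoxon and U ≤ 23 for Mann-Whitney.

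| *d* | *d*√10 | Paired t, fall in VR | Wilcoxon, fall in VR | Wilcoxon: VR significant, control not | Mann-Whitney on change favours VR | Both clauses met |
|---|---|---|---|---|---|---|
| 0 | 0 | 2.5% | 2.4% | 2.4% | 2.2% | 0.7% |
| 0.2 | 0.63 | 8.2% | 7.9% | 7.3% | 2.2% | 1.3% |
| 0.3 | 0.95 | 13.4% | 13.0% | 11.3% | 2.2% | 1.6% |
| 0.5 | 1.58 | 29.3% | 28.4% | 20.5% | 2.2% | 2.0% |

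The within-group result moves with the natural course. The between-group result does not.

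The unit matters. The SD of change is √(2(1−*r*)) score SDs, where *r* is the pre-post correlation. At *r* = 0.5 the two units coincide. At *r* = 0.7 it is √0.6 = 0.77, so a fall of 0.5 score SD is 0.5/0.77 = 0.65 SD of change, and the paired t rate becomes 45%.

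**Step 2: baseline adjustment.** Take a score SD of 1 and a true difference of 0.8. The standard error is √(*v* × 2/10), with:
- post scores: *v* = 1, 18 df
- change scores: *v* = 2(1−*r*), 18 df
- ANCOVA: *v* = (1−*r*²)(1 + 1/16), 17 df

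At *r* = 0.5, *v* = 1, 1 and 0.75 × 1.0625 = 0.797. The standard errors are 0.447, 0.447 and 0.399, and the noncentralities (0.8 divided by each) are 1.79, 1.79 and 2.00. Power from the noncentral t:

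| *r* | Post | Change | ANCOVA | Gain over the better unadjusted test |
|---|---|---|---|---|
| 0.3 | 39.5% | 29.9% | 40.4% | 0.9 points |
| 0.5 | 39.5% | 39.5% | 47.2% | 7.7 points |
| 0.7 | 39.5% | 58.9% | 63.0% | 4.1 points |

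The mean 95% CI half-width is 0.93 SD for post scores. For change scores it is 0.93 × √(2(1−*r*)) = 1.10, 0.93 and 0.72 SD at *r* = 0.3, 0.5 and 0.7. For ANCOVA it is 0.91, 0.83 and 0.68 SD.

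**The case against.** **The hypothesis is already comparative.** The clauses are joined by *and*, the second qualifies the same reduction, objective 1 is against control, and *Study design* ties the hypothesis to the randomised groups. This stands. A reader might infer that natural decline could confirm the hypothesis. It could not: with no VR effect both clauses are met in only 1.3% to 2.0% of trials at the declines considered, below the 2.2% for the between-group test alone.

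**The harm is conjecture about reporting.** This largely stands. The protocol does not say that a within-VR p-value will be presented as an effect, nor that significance will be compared between arms, so the 7% to 20% figures describe a practice it does not propose. What remains is that the wording leaves the first clause open to separate reporting, and nothing in the analysis section closes it.

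**The size of the decline is unknown.** This stands. The introduction gives no rate and nothing over four weeks, so 28% depends on an assumed fall of 0.5 SD of change. The argument is also weakest for grief, which the intervention chiefly addresses.

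**Covariates belong in a statistical analysis plan, and change scores already use baseline.** This partly stands. Such a plan, not at hand, could add a covariate, and the second clause may well mean change scores. A reader might infer that baseline is ignored or that the unadjusted tests are biased. The text supports neither: it does not say which score is compared, and randomisation keeps both versions valid. But the protocol itself names its between-group tests, and neither takes a covariate, so naming a more precise analysis is a fair improvement.

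**Conclusion.** The point holds in limited form, at minor severity. The first clause can be met alone on PCL-5 or HADS without a VR effect, in about 8% to 28% of trials for an assumed shared fall of 0.2 to 0.5 SD of change. That rests on 10 per arm, two-sided 5%, normal data and a four-week decline the protocol does not quantify. The full hypothesis and the randomised comparison are sound.

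The baseline part concerns efficiency, not validity. Over the better unadjusted test, ANCOVA gains about 8 points of power at a correlation of 0.5, 4 points at 0.7 (half-width 0.68 SD against 0.72 SD for change scores) and almost nothing at 0.3. Because the better unadjusted test depends on a correlation not known in advance, ANCOVA also avoids having to choose between post and change scores. The trial stays imprecise either way: 80% power needs a difference of about 1.32 SD unadjusted, and about 1.2 SD (correlation 0.5) or 1.0 SD (0.7) with ANCOVA.

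**What to change.** In *AViR Project*, word the hypothesis as one comparative claim, for example: after the intervention, and adjusting for baseline, scores for grief, depression, anxiety and post-traumatic stress will be lower in the VR group than in the control group.

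In *Data processing and analysis*, add:
- Any claim about an effect of VR rests on the between-group comparison of post-intervention scores adjusted for baseline (ANCOVA), given as a difference with 95% CI.
- The Mann-Whitney test on change scores is the nonparametric alternative.
- Within-group changes are reported descriptively for both groups (mean change with 95% CI). No conclusion about VR is drawn from within-group p-values, and significance is not compared between groups.

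The cost is one sentence and one paragraph. No new data or visits are needed, since both groups already give both assessments. There are two downsides: a significant within-VR fall can no longer be offered as evidence of effect, and ANCOVA assumes a common linear slope on baseline that 10 women per arm can hardly check.

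### Women may enter from just after the loss to six months later, but time since loss is used neither in the stated allocation nor in the stated between-arm tests: avoidable noise, modest in size and cheap to remove

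*Protocol*

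**What the plan says.** - **Entry window** (Protocol, Inclusion and exclusion criteria): "Have experienced an involuntary gestational loss in the first 20 weeks of pregnancy, in the last six months". There is an upper limit and no lower one.
- **Size** (Sample and recruitment): "We intend to recruit a sample of 20 participants who will later be divided into two groups". No allocation ratio is given.
- **Allocation** (Study design): "Participants who meet the inclusion criteria will be randomly allocated to one of the two groups described". No stratum, block or minimisation factor is named.
- **Natural course** (opening background, on a cohort of 492 women): "after one month, 29% had symptoms of post-traumatic stress, 24% symptoms of moderate/severe anxiety, and 11% symptoms of moderate/severe depression", and then "these decreased over time but were still clinically relevant nine months after the loss". The rate of decline is not given. On grief, the same text says that an early loss "can lead to chronic grief that goes on for years, not showing the typical decline of grief seen in other situations".
- **Follow-up** (Data collection procedure): "The pilot study will encompass a 4-week intervention and two evaluation moments: pre-intervention (baseline) and post-intervention".
- **Hypothesis** (AViR Project): symptoms fall with VR, and "this reduction will be significantly superior when compared to the control group".
- **Analysis** (Data processing and analysis): t, Wilcoxon and Mann-Whitney tests at 5%, with no covariate.

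**The concern.** A woman a few days after her loss and another at 26 weeks are equally eligible, yet the treatment period is only four weeks. For three of the four symptom domains measured (post-traumatic stress by PCL-5, anxiety and depression by HADS), the protocol itself describes spontaneous improvement across months that overlap the entry window. Where a woman stands on that course at entry affects her expected score. If recovery slows with time, it also affects her expected change over the next four weeks.

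With about 10 women per arm, chance can leave one arm with clearly more recent losses. That woman-to-woman variation then goes into the error of the between-arm comparison, although the factor behind it is known before allocation: eligibility cannot be judged without it. The stake is the precision of objective 1, the comparison with usual follow-up.

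**Working it through.** The protocol gives no figure on balance or rate of recovery to reproduce. Its sample size of 20 comes without effect size, SD or power.

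**Assumptions, not in the protocol:** 10 per arm; time since loss uniform over 0 to 26 weeks; outcome SD 1.

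**1. How far apart can the arms be?**
- SD of the arm difference in mean time since loss = 26/√12 × √(2/10) = 7.51 × 0.447 = 3.36 weeks.
- Simulation (200,000 allocations): the difference exceeds 4 weeks in about 23%.
- If 10 of the 20 losses are recent, a 7:3 split or worse has probability 2 × 16,526/184,756 = 17.9%.

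**2. What does stratifying at 13 weeks do?** With five women per arm in each stratum, SD = 13/√12 × √(2/10) = 1.68 weeks. The chance of a gap above 4 weeks falls to about 1.6%.

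**3. What is a gap worth in symptom units?** Assume the mean symptom level above its floor is A·exp(−kt), with A = 1 to 2 SD at the loss and k = ln 2 / half-life, half-life 1 to 6 months.
- Example: A = 2, half-life 2 months (8.67 weeks), so k = 0.080 per week. The fraction lost in four weeks is 1 − exp(−0.32) = 0.274. At 2 weeks the level is 1.70 SD and four-week change 0.47 SD; at 22 weeks they are 0.34 and 0.09 SD.
- Over the whole grid, given a gap above 4 weeks, the mean absolute shift in the arm difference is about **0.01 to 0.16 SD for change** and **0.09 to 0.26 SD for post-treatment scores**.
- The two shifts have opposite signs. The arm with more recent losses shows more decline but ends with higher scores.
- For comparison, the standard error of an arm difference is √(2/10) = 0.45 SD.

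**4. What happens to the tests?** Let ρ be the assumed correlation between time since loss and the outcome analysed (20,000 simulated trials per setting).

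| | ρ = 0.3 | ρ = 0.5 | ρ = 0.7 |
|---|---|---|---|
| Type I error, simple allocation, unadjusted t, all allocations | about 5% | about 5% | about 5% |
| Same, given a gap above 1 month | 7% | 11% | 16–17% |
| Power at 0.8 SD, simple allocation, unadjusted | 39% | 39% | 40% |
| Power at 0.8 SD, simple allocation, adjusted | 40% | 47% | 64% |
| Type I error, stratified but unadjusted | 4.1% | 3.3% | 1.5% |

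At ρ = 0, adjusting costs a little: power at 0.8 SD goes from 39% to 37%.

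**5. Which ρ is credible?** In step 3 the individual SD due to time since loss is at most about 0.24 for change and 0.36 for post-treatment scores. With residual SD 1, ρ is at most 0.24/√(0.24² + 1) = 0.23 and 0.36/√(0.36² + 1) = 0.34. The 0.5 and 0.7 columns therefore show what a strong relation would do; the recovery curves assumed here do not reach them.

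**The case against.** The strongest reply has five parts.

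- **Randomisation already covers this.** Correct on average: chance imbalance is part of what the 5% error rate allows for. A reader might infer that the open window biases the trial towards or against VR. The documents do not support that. What remains is lost precision, and a less reliable result when the one allocation obtained happens to be uneven.
- **The background speaks of level, not rate.** Also correct. A reader might infer that natural change over four weeks must depend on entry time. The text says only that symptoms decreased. If the decline is linear, four-week change is the same whenever a woman enters, and imbalance affects post-treatment scores only. A large distortion of change would need steep early recovery, for which the protocol gives no figure.
- **Grief may not follow this course.** The background says so, and grief is what the prototype targets. The point is weak for the Perinatal Grief Scale and rests on the other three domains.
- **The protocol is silent on the procedure rather than committed to simple randomisation.** True, and an SAP could add adjustment. But an analysis plan cannot restore balance after allocation, and the tests now named carry no covariate.
- **It is a pilot of 20, and other factors could be argued as strata.** With 10 per arm, 80% power needs an effect of about 1.33 SD, so this factor is not the main limit on objective 1. Still, the protocol chose to test superiority over control, and time since loss is the factor along which its own background describes symptoms falling across the entry window.

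**Conclusion.** The point holds as a modest, inexpensive improvement in precision. Three facts are in the text: a window of 0 to 6 months, symptoms in three domains that fall over time, and no use of time since loss in the stated allocation or tests. A gap between arms longer than the four-week intervention arises in about 23% of allocations if entry is uniform and the arms are equal.

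In symptom units, such a gap is worth a fraction of the standard error: 0.01 to 0.16 SD for change and 0.09 to 0.26 SD for post-treatment scores, against 0.45 SD. These ranges depend on the assumed exponential course and entry pattern; steeper early recovery would enlarge them. That the imbalance would by itself produce an apparent VR effect, or hide a real one, is not shown. Nothing here invalidates the trial.

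**What to change.** 1. **Allocation.** Stratify at three months since loss (up to three, over three), with concealed lists and randomly varied block sizes. Alternatively, minimise on weeks since loss with a random element.
2. **Reporting.** Record weeks since loss at baseline and show it by arm.
3. **Analysis.** Compare the arms in a model with treatment, baseline score and time since loss. This step belongs with the first: stratifying while keeping the unadjusted test makes it conservative (type I error 4.1%, 3.3% and 1.5% at ρ = 0.3, 0.5 and 0.7).

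**Cost.** Two lists instead of one and no new data, since the date of loss is needed for eligibility anyway. The model uses one or two degrees of freedom. Unfilled blocks can leave the arms slightly unequal in number. In strata of about ten women, fixed small blocks would make some assignments predictable, hence the varied sizes and concealment. If time since loss is only weakly related to change, the gain will be small.
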